Because this is a feasibility study, primary outcomes of interest are recruitment (consent) rate, time required to complete initial tele-medicine assessment in the ED, time needed to administer XR-NTX in the ED, total ED length of stay, time to first follow up after the initial ED encounter, number of cell phones issued by the study, retention and follow up rates over the 3-month study

period, retention rate with other providers in San Francisco, number of doses of XR-NTX received during the study period and intervals between doses, and barriers to and facilitators of follow-up after the initial ED visit.

We will also collect pilot data on the following for statistical analysis:

Predictor Variable: Multi-modal treatment with Extended Release Naltrexone and case management

Primary Outcome: Change in the number of Emergency Department visits for alcohol-related complaints. [(# of ED visits for alcohol related complaint in 12 months after enrollment) - (# of ED visits for alcohol related complaint in 12 months before enrollment)].

Secondary Outcomes: number of standard alcoholic drinks consumed per week, number of days of heavy drinking, overall substance use severity (change in AUDIT score), change in alcohol-related social/occupational/psychological problems identified on SIP-2R, change in PEth, and change in urine ethyl glucuronide

Cost analysis: This study will not provide precise estimates of efficacy or costs. However, we will use our results to perform a basic cost analysis to guide future research. We will estimate: overall cost and cost per patient (medications, case management, follow-up visits), cost per avoided ED visit, cost per avoided hospitalization, program cost vs expected medical cost saved. All costs will be estimated at the societal perspective

Potential confounding variables or covariates, justifications:

There are several potential confounders which we will measure such as number of doses of XR-NTX received, willingness to change, engagement in other, baseline substance use severity, housing status, psychiatric and medical comorbidity, and basic demographic variables such as age and sex. The primary strategy employed to combat these cofounders is the selection of the primary outcome. Since the outcome is a change from the patient's baseline ED usage from the prior year each patient serves as their own control. Thus they are matched for many of the possible confounders.

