The risk of bias is substantial given that all enrollees are to be treated with XR-NRT and the study is not randomized or blinded and the population of interest is at high risk of being lost to follow up. We intend to conduct both an intention to treat analysis and a per protocol analysis, though our sample size may limit the utility of this approach. We will employ an independent data analyst to collect the ED visit counts and perform the final statistical analysis.

Statistical issues:

Statistical Test: Paired T Test

Hypothesis:

ED initiated Treatment of alcohol use disorders with multi-modal therapy reduces alcohol related ED visits in patients with frequent ED visits for alcohol related complaints

Sample Size:

We will enroll 25 patients. As a feasibility study our sample size was chosen as it represents a reasonable patient load for a single case manager. Because this population is difficult to retain in treatment, we anticipate the drop-out rate will be significant. Patients who drop out of the study (either withdraw or are lost to follow up) will be replaced with new enrollees until 25 patients have been recruited into the study. The goal of this practice is to maximize the benefit to the patient population, avoid wasting donated study medication, and to allow the research team to optimize recruitment and retention strategies.

Last year 42 patients presented to the UCSF Emergency Department at least 4 times for an alcohol related complaint. Of this group the mean number of visits was 8.49 with a SD of 8.58. The median number of visits was 6. The number of visits ranged from 4-47. After excluding 2 outliers (40 and 47 visits, each $> 3SD$ above the mean) the mean was 6.78 visits with a SD of 3.5 visits.

We estimate a standardized effect size of 0.584 would represent 2-5 emergency visits for alcohol related complaints. This equates to a 29-59% reduction in ED utilization, which is clinically relevant.

Data management plan:

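### The 2-visit (29%) end of the stated effect range rests on an SD with two heavy users removed whom the analysis would keep, and neither end uses the SD of within-patient change

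*Combined protocol and SAP*

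**What the plan says.** Section IV (Analysis, Measurements, and Outcomes) defines the pilot outcome as a change score: "Primary Outcome: Change in the number of Emergency Department visits for alcohol-related complaints", the 12 months after enrolment minus the 12 months before. Under Statistical issues the test is given as "Statistical Test: Paired T Test".

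The Sample Size text explains the number enrolled on practical grounds: "our sample size was chosen as it represents a reasonable patient load for a single case manager". It then describes a reference group from one year of UCSF data: "Last year 42 patients presented to the UCSF Emergency Department at least 4 times for an alcohol related complaint". For everyone in it, "Of this group the mean number of visits was 8.49 with a SD of 8.58". After two patients with 40 and 47 visits are set aside as more than 3 SD above the mean, "the mean was 6.78 visits with a SD of 3.5 visits".

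The sensitivity statement follows: "We estimate a standardized effect size of 0.584 would represent 2-5 emergency visits for alcohol related complaints". And then: "This equates to a 29-59% reduction in ED utilization, which is clinically relevant". The text does not say which SD produces which end of the range. It states neither a significance level nor a power.

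**The concern.** There are two problems with how 0.584 becomes visits.

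First, the favourable end appears to come from the trimmed data. Heavy ED users are the population the study is aimed at. The Inclusion and Exclusion Criteria in Section II set a minimum number of visits and no maximum. Section IV plans intention-to-treat and per-protocol analyses with no outlier rule. Patients like the two removed could enrol and would be analysed. The removal is disclosed, but the text does not say that the 29% depends on it.

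Second, both SDs measure how patients differ from one another within one year. A paired t test is governed by how much each patient's count changes between years. That SD, or the before-after correlation from which it could be derived, appears nowhere.

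This is the only statement of what change 25 patients could show. If 29% is taken at face value, a non-significant fall near 30% could be misread as evidence against an effect, and the figure could be carried into the randomised trial foreseen in Section VI.

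**Working it through.** **Inputs (Section IV, Sample Size).** Effect size 0.584; n = 25; all patients: mean 8.49, SD 8.58; two removed: mean 6.78, SD 3.5.

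**1. Where 0.584 comes from.** Using the noncentral t with n = 25 (24 degrees of freedom), a two-sided 5% paired t test has 80% power at d = 0.58403. Other usual choices do not match: one-sided 80% gives 0.512, one-sided 90% gives 0.603, two-sided 90% gives 0.676. Two-sided 5% and 80% power are therefore inferred, not stated.

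**2. Reproducing the range.** Visits = 0.584 x SD; percentage = visits / mean of the same data.
- Two removed: 0.584 x 3.5 = 2.04 visits. Rounded, 2 / 6.78 = 29.5%; unrounded, 2.04 / 6.78 = 30.1%. This is the lower end.
- All kept: 0.584 x 8.58 = 5.01 visits; 5.01 / 8.49 = 59.0%. This is the upper end.

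The range is one calculation done with and without two patients. The trimmed mean matters too: 2.04 / 8.49 would be 24%.

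**3. Weight of the two patients.** They account for (40 + 47) / (42 x 8.49) = 87 / 356.6 = 24% of visits. Their share of the sum of squares about the mean is [(40 - 8.49)² + (47 - 8.49)²] / (41 x 8.58²) = 82%. (The stated means fit 43 patients slightly better than 42; with 43 the shares are 24% and 80%.)

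**4. The SD the test needs.** With equal variances and year-to-year correlation r, SD of change = SD x √(2(1 - r)). This equals the one-year SD only when r = 0.5. Above 0.5 the one-year SD overstates the detectable fall; below 0.5 it understates it.

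**5. Illustration, all patients kept.** The correlation, the variance model and approximately normal changes are all assumed here. In the second model the after-year SD shrinks with the fall: SD of change = 8.58 x √(1 + k² - 2rk), with k = 1 - fall.

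| r | Detectable fall, equal SDs | Detectable fall, scaled SD | Power for a 29% fall (0.29 x 8.49 = 2.46 visits), equal / scaled |
|---|---|---|---|
| 0.2 | 6.3 visits (75%) | 5.0 visits (59%) | 19% / 24% |
| 0.5 | 5.0 visits (59%) | 4.3 visits (51%) | 28% / 34% |
| 0.8 | 3.2 visits (37%) | 3.1 visits (37%) | 59% / 62% |

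At r = 0.9 the detectable fall is 26% (equal) or 28% (scaled).

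**6. Limit of the normal-theory figures.** An illustrative simulation used an invented cohort close to the reference group (43 patients, mean 8.47, SD 8.59, median 6, including 40 and 47). After-year counts were Poisson with gamma variation and a 29% mean fall. Actual paired-t power against the normal-theory value was 41% v 25% at r = 0.56, and 74% v 63% at r = 0.80. The power figures in the table may therefore be too low for counts this skewed.

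**The case against.** The strongest reply is that nothing is hidden and little depends on the range. Both SDs are printed, the two patients and the reason for removing them are given, and the upper end already keeps everyone. The sample size came from workload, feasibility measures come first, Section IV says efficacy estimates will not be precise, and no decision rule uses 29%. All of this stands, and it limits the consequence. It does not mend the sentence, which offers 29% as what the effect size represents without the condition it needs.

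It can also be said that 25 enrollees might include no such patient. If 2 in 42 are like this, the chance is about 16% (drawing without replacement: 17 x 16 / (42 x 41)) to 30% (independent draws: (40/42)^25). That is a chance outcome of recruitment, and a planning figure should not be conditional on it.

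A reader might infer something stronger: that 29% is out of reach unless r is about 0.88-0.89, or that the detectable fall is 75%, 59% or 37%. The documents do not support either as fact. Those values rest on an assumed correlation, an assumed variance model and normal changes, and the skewed-count simulation shows that actual power can be higher. At high r, 29% lies within the all-patient range. Nor do the documents support reading this as a flaw in the choice of 25 patients.

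The entry threshold is at least 3 visits in some places (Initial Screening, Inclusion Criteria) and at least 4 in others (Determination of Eligibility, Study Subjects). Those passages need reconciling, and the reference count of 42 needs confirming, but both are side issues.

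**Conclusion.** The point holds as a mis-specified sensitivity statement. The attribution of the 2-visit/29% end to the trimmed SD of 3.5, and of the 5-visit/59% end to the full SD of 8.58, is inferred from arithmetic, but both ends reproduce. No rule in the plan removes the patients whose deletion produces the lower end. Neither SD is the one the paired t test uses, and the size and direction of that error cannot be determined from the documents.

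With equal variances, r = 0.5, two-sided 5% and 80% power, the all-patient figure is about 5 visits (59%). It is a stand-in and not an established detectable difference. The impact is confined to interpreting the pilot ED-visit result and planning the follow-up trial.

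**What to change.** Stop presenting 29% as what 25 patients can show with all patients kept. Suggested replacement, once the significance level and power are confirmed:

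> With 25 pairs, 0.584 is in units of the SD of within-patient change (two-sided 5%, 80% power), and that SD is not known. Using the all-patient one-year SD as a stand-in (equal variances, correlation 0.5) gives about 5 visits (59%). On the same stand-in, the 2-visit (29-30%) figure applies only if the two highest users are excluded, which the analysis does not do.

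If a range over the correlation is added (for example about 37% at r = 0.8 to 59-75% at r = 0.2), label it illustrative. Say that it depends on the assumed correlation, the variance model and approximately normal changes, and that with skewed counts actual power can be higher. Better still, use an observed SD of change if a second year of UCSF counts exists; the protocol describes only one.

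Keep N = 25, the paired t test and the mean change. The cost is wording, plus a data extract if a second year is used. The downside is that the stated sensitivity becomes less favourable and visibly dependent on assumptions.
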